## 7.9 Interim Analysis

No formal interim analysis is planned in this study.

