**Table 2: Binomial Probabilities of Dose-Limiting Toxicity in a Cohort of 9 Patients**

K	Binomial Probability		
	Exactly k DLTs	≤ k DLTs	>k DLTs
0	0.0260	0.0260	0.9740
1	0.1171	0.1431	0.8569
2	0.2341	0.3772	0.6228
3	0.2731	0.6503	0.3497
4	0.2048	0.8552	0.1448
5	0.1024	0.9576	0.0424
6	0.0341	0.9917	0.0083
7	0.0073	0.9990	0.0010
8	0.0009	0.9999	0.0001
9	0.0001	1.0000	0.0000

DLT=dose-limiting toxicity; k=number of dose-limiting toxicities

For the Phase 2 PD-1/PD-L1 Inhibitor Refractory cohort, the sample size of approximately 20 patients will be evaluated for initial evidence of activity in this PD-1/PD-L1 refractory population.

For the Phase 2 prOVCA cohort, a Simon’s 2-stage optimal design (Simon 1989) will be used in the MSS/MMR-proficient prOVCA population. The null hypothesis of the true response rate is

15% will be tested at one-sided type I error rate of 10%. The alternative hypothesis is the true response rate is at least 35%. Accrual of patients in Stage 1 will continue until 9 evaluable MSS/MMR-proficient patients have been enrolled, with evaluable defined as having received at least one dose of study drug. The analysis for Stage 1 will not occur until all evaluable patients in Stage 1 have had the opportunity to have at least 2 post-baseline tumor assessments (or have discontinued tumor assessments beforehand). If there are fewer than 2 responders in these 9 patients, enrollment into this cohort of the study will be stopped. Otherwise, 14 additional patients will be accrued during Stage 2, for a total of 23 patients enrolled in this cohort. The null hypothesis will be rejected if 6 or more responses are observed in 23 patients. With this sample size, the actual Type I error is 9.9%, and the power is 80%. If the null hypothesis is true, the expected sample size is 15 patients, and the probability of stopping enrollment into this cohort of the study early is 60%. Patients who are MSI-H/mismatch repair-deficient (dMMR) will not be included in the Simon's 2-stage analyses and the study will ensure that the sample size requirements are met by enrolling the required number of MSS/MMR-proficient pOVCA patients.

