For the Phase 2 PDA cohort, a Simon's 2-stage optimal design ([Simon 1989](#)) will be used in the MSS/MMR-proficient PDA population. The null hypothesis of the true response rate is 4%, versus alternative of 15%. Accrual of patients in Stage 1 will continue until 15 evaluable MSS/MMR-proficient patients have been enrolled, with evaluable defined as having received at least one dose of study drug. The analysis for Stage 1 will not occur until all evaluable patients in Stage 1 have had the opportunity to have at least 2 post-baseline tumor assessments (or have discontinued tumor assessments beforehand). If there are no responders in these 15 patients, enrollment into this cohort of the study will be stopped. Otherwise, 14 additional MSS/MMR-proficient patients will be accrued during Stage 2, for a total of 29 patients enrolled in this cohort. The null hypothesis will be rejected if 3 or more responses are observed in 29 MSS/MMR-proficient patients. With this sample size, the actual Type I error is 9.9%, and the power is 80%. If the null hypothesis is true, the expected sample size is 21 patients, and the probability of stopping enrollment into this cohort of the study early is 54%. PDA patients who are MSI-H/dMMR will not be included in the Simon's 2-stage analyses and the study will ensure that the sample size requirements are met by enrolling the required number of MSS/MMR-proficient PDA patients.

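### SAP 7.9 denies the Stage 1 looks that SAP 3.2 requires, and SAP 5.3/7.5 puts the prOVCA and PDA primary ORR in all treated patients instead of MSS/MMR-proficient patients

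*SAP*

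**What the plan says.** **Interim analysis.** SAP 7.9 consists of one sentence: "No formal interim analysis is planned in this study". SAP 3.2 describes Simon two-stage designs for prOVCA and PDA and gives the first look its own timing: "The analysis for Stage 1 will not occur until all evaluable patients in Stage 1 have had the opportunity" for two or more post-baseline tumor assessments. The consequence is mandatory. For prOVCA: "If there are fewer than 2 responders in these 9 patients, enrollment into this cohort of the study will be stopped". For PDA: "If there are no responders in these 15 patients, enrollment into this cohort of the study will be stopped". The final rules follow. For prOVCA: "The null hypothesis will be rejected if 6 or more responses are observed in 23 patients". For PDA: "The null hypothesis will be rejected if 3 or more responses are observed in 29 MSS/MMR-proficient patients". Both cohorts are quoted an actual type I error of 9.9% and power of 80%. A nominal level (one-sided 10%) is given for prOVCA only.

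**Population.** SAP 2.1 words the prOVCA and PDA primary objectives for MSS/MMR-proficient patients. SAP 3.2 says of prOVCA that "Patients who are MSI-H/mismatch repair-deficient (dMMR) will not be included in the" Simon analyses, and says the same for PDA. SAP 5.3 defines the FAS as every patient given any dose of either drug and assigns it all efficacy analyses; SAP 7.5 repeats that assignment. SAP 7.5.1 gives ORR based on confirmed responses with an exact 95% CI. It mentions no Simon cut-off and no MSS/MMR restriction. None of the sets in section 5.0 is restricted by MSI/MMR status, and SAP 7.1.7 tabulates Phase 2 by cohort only.

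**The concern.** The section a reader would consult about interim looks says there are none, yet the quoted error rate depends on two of them. An analysis of accumulating primary-endpoint data that decides whether a cohort goes on enrolling is an interim analysis in the ordinary sense. If the word formal was meant to set futility looks aside, the SAP does not say so.

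The population mismatch bears on the primary estimate. Protocol 9.3 plans extra enrolment to make up for patients found to be MSI-H/dMMR, and Protocol 7.1.5 has status confirmed by retrospective central testing. Some treated patients are therefore expected to fall outside the target population but inside the FAS. A programmer working from SAP sections 5 and 7 would report a primary ORR and CI that include them, and would have no analysis set or table for the population named in the objective.

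**Working it through.** **Inputs (SAP 3.2).** prOVCA: n1 = 9, stop at 1 or fewer, n = 23, reject at k = 6, null 15%, alternative 35%. PDA: n1 = 15, stop at 0, n = 29, reject at k = 3, null 4%, alternative 15%.

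**Step 1: reproduce the plan's figures.** With r1 the largest Stage 1 count that stops enrolment, the rejection probability is the sum over x1 > r1 of P(X1 = x1) × P(Bin(n − n1, p) ≥ k − x1).

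- prOVCA at 15%: x1 = 2 gives 0.25967 × 0.14651 = 0.03804; x1 = 3 gives 0.10692 × 0.35209 = 0.03765; x1 = 4 gives 0.02830 × 0.64333 = 0.01821; x1 = 5 gives 0.00499 × 0.89723 = 0.00448; x1 ≥ 6 gives 0.00063. The sum is 0.0990.
- PDA at 4%: x1 = 1 gives 0.33880 × 0.10593 = 0.03589; x1 = 2 gives 0.09882 × 0.43533 = 0.04302; x1 ≥ 3 gives 0.02029. The sum is 0.0992.

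Expected sample size under the null is n1 + (1 − early-stop probability) × (n − n1).

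| | Type I error | Power | Early stop under null | Expected N under null |
|---|---|---|---|---|
| prOVCA, recomputed | 9.90% | 80.4% | 59.9% | 14.6 |
| prOVCA, stated | 9.9% | 80% | 60% | 15 |
| PDA, recomputed | 9.92% | 80.1% | 54.2% | 21.4 |
| PDA, stated | 9.9% | 80% | 54% | 21 |

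Everything agrees at the printed precision.

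**Step 2: what the figures depend on.** Take SAP 7.9 literally: no Stage 1 stop, same final cut-offs. The sample paths that the stop would have ended are added back.

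- prOVCA: 0 or 1 responder in Stage 1 but at least 6 overall has probability 0.00267 + 0.01719 = 0.01986. Type I error is 0.0990 + 0.0199 = 0.1189, that is P(Bin(23, 0.15) ≥ 6).
- PDA: 0 responders in Stage 1 but at least 3 overall has probability 0.54209 × 0.01672 = 0.00907. Type I error is 0.0992 + 0.0091 = 0.1083, that is P(Bin(29, 0.04) ≥ 3).

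The first exceeds the stated one-sided 10%. The second exceeds PDA's stated 9.9%, with no nominal level given for comparison.

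**Step 3: population of the primary ORR.** The SAP sections set side by side:

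- 2.1: objective in MSS/MMR-proficient patients.
- 3.2: test in treated MSS/MMR-proficient patients, MSI-H/dMMR excluded.
- 5.3, 7.5, 7.5.1: ORR and CI in all treated patients.
- 5.0: no set corresponding to 2.1 and 3.2.

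Suppose, as an assumption, that one MSI-H patient is treated beyond the planned MSS/MMR-proficient number and responds. With 2 MSS responders in PDA, the ORR for the stated objective is 2/29 = 6.9%, while 7.5.1 would report 3/30 = 10.0%. In prOVCA, 5/23 = 21.7% would become 6/24 = 25.0%.

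**Step 4: illustration only, if the cut-offs were applied to the FAS count.** Assume exactly one such extra patient, with response probability q, MSS patients at the null rate, and Stage 1 judged on MSS patients. Type I error is then α + q × P(Stage 1 passed and exactly k − 1 MSS responses). That last probability is 0.0922 (prOVCA) and 0.1674 (PDA). For q from 0 to 1 the ranges are 9.9% to 0.0990 + 0.0922 = 19.1% (prOVCA), and 9.9% to 0.0992 + 0.1674 = 26.7% (PDA).

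**The case against.** The strongest reply is that SAP 3.2 already holds everything needed: Stage 1 size, timing, stopping rule, final cut-offs and the exclusion of MSI-H/dMMR patients. A specific rule reasonably governs a general sentence. A futility-only gate that belongs to the design might not be called a formal interim analysis, and SAP 1.0 says the document covers the final analysis. The primary objective is to estimate efficacy, so an ORR with a CI is a proper primary summary.

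Much of this stands, and it rules out three stronger readings.

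- A reader might infer that Stage 1 will be skipped and the true type I error is 11.9% or 10.8%. The mandatory wording in 3.2 makes that unlikely; those figures show only what the 9.9% rests on.
- A reader might infer that the go/no-go decision will be made on the FAS, with error rates of 19% to 27%. SAP 3.2 forbids that count, and the documents give no MSI-H/dMMR prevalence with which to weight the scenario.
- A reader might infer that the designs are miscalculated or the 95% CI is wrong. The designs reproduce exactly, and Protocol 11.1.2.1 specifies the exact 95% CI. Only the population in which the CI is computed is at issue.

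The reply does not settle two things. SAP 3.2 itself calls the look an analysis, and 7.9 makes no exception for it. And the exclusion in 3.2 is worded for the Simon analyses; it does not move the ORR and CI of 7.5.1 off the FAS. If the objective is estimation, the population of that estimate matters all the more.

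**Conclusion.** The point holds as a minor to moderate internal inconsistency in the SAP. First, 7.9 contradicts 3.2, and the stated 9.9% type I error requires the looks that 7.9 denies. Second, the primary ORR and its CI in prOVCA and PDA are assigned to all treated patients, a different population from the one in the primary objective and the Simon test, and no analysis set bridges the two. No design figure is wrong, and the documents do not suggest that Stage 1 will be omitted or the cut-offs misapplied.

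Both conflicts lie between sections of the SAP itself. The expectation that MSI-H/dMMR patients will be treated comes from protocol Version 4, whereas the SAP cites Version 5, which was not available; on that point the protocol is supporting evidence. How far the FAS estimate would depart from the MSS/MMR-proficient one depends on how many such patients are treated, and the documents do not give that number.

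**What to change.** - **SAP 7.9:** state that the Stage 1 Simon futility analyses for prOVCA and PDA, as specified in 3.2, are the only planned interim analyses.
- **SAP 5.0:** define an MSS/MMR-proficient analysis set of treated patients with that status. State how patients of unknown status are handled, because Protocol 5.2.1 (criterion 11) and 7.1.5 allow the tissue requirement to be waived.
- **SAP 7.5/7.5.1:** in these two cohorts, make that set the population for the primary ORR, its 95% CI and the Simon decision (at least 6/23 and at least 3/29). Keep the FAS ORR as a supplementary summary.
- **Stage 1 count:** say whether it uses confirmed responses. SAP 7.5.1 bases the primary analysis on confirmed responses; 3.2 does not say which kind Stage 1 counts.

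The cost is one extra analysis set, one extra ORR row for each of the two cohorts, and a few sentences, to be settled before database lock. No cut-off, sample size or operating characteristic changes.

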## 8.0 DATA AND ANALYSIS QUALITY ASSURANCE

This protocol was conducted under the sponsorship of Array BioPharma. Personnel within Array BioPharma or CRO designee provided statistical and data management input for the design of the clinical trial protocol; data management, statistical analysis and generation of tables, listings and figures; and medical writing support for the clinical study report.

All parties mentioned above will work diligently and collaboratively to ensure that data collection and analysis for this study are of the highest quality. This will be accomplished through programmed edit checks, quality control processes, and clinical and statistical review of data displays. Quality and accuracy of statistical analyses will be verified through established statistical programming validation processes.

## **10.0 STANDARD OPERATING PROCEDURES, FORMS AND WORK INSTRUCTIONS**

Array Biopharma SOPs will be utilized.
